### **Intervention:**

- Cure guideline control group- cleansing exit orifice with physiological saline (0.9%), drying with sterile gauze, disinfection with 2% water-based chlorhexidine solution, environmental drying for 30 seconds and covering with self-adhesive semi-permeable polyurethane dressing.
- Cure guideline experimental group - cleaning of the exit orifice with physiological saline (0.9%), drying with sterile gauze, application of a semi-permeable polyurethane dressing with 2% self-adhesive chlorhexidine gluconate, centering the chlorhexidine gluconate band well in the exit orifice.

Outflow orifice curettage will be performed by experienced nurses from our hemodialysis unit, after a briefing on the study methodology. In both cases the treatment will be performed weekly (first day of the week), or whenever there is exudate from the exit site or detachment of the dressing; before connecting the catheter to the hemodialysis monitor. In both cases, the treatment will be carried out under maximum aseptic measures: previous hand hygiene, sterile material and treatment, and use of masks by the patient, nurse and nursing assistant. The connection to the hemodialysis monitor will be performed under these aseptic measures, covering the connection between the lines and the catheter with gauze impregnated with 2% water-based chlorhexidine solution and a sterile cloth. In addition, a bioconnector is used for hemodialysis catheters.

**Population:** patients on renal replacement therapy with hemodialysis whose vascular access is an indwelling catheter. Fifty patients will be included (25 patients in the control group - chlorhexidine 2% solution and covered with self-adhesive transparent polyurethane dressing - and 25 patients in the experimental group - with self-adhesive ACG dressings). The sample size calculation was performed with the GRANMO program version 7.12, accepting an alpha risk of 0.05 and a beta risk of 0.2 in a bilateral contrast, to detect as statistically significant the difference between two proportions, which for the control group is expected to be 25% and the experimental group 5%. A loss-to-follow-up rate of 10% has been estimated.

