#### **Inclusion criteria:**

- Be included in hemodialysis program in our unit.
- Be a carrier of a catheter as vascular access, inserted 1 month prior to inclusion in the study.
- Remain on hemodialysis treatment for at least 3 months at the dialysis center
- Consent to participate in the study.

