#### **Variables:**

- a) **Patient clinical variables**- age, sex, etiology of renal disease according to ERA/EDTA code, degree of comorbidity according to the modified Charlson Index for patients with renal disease, time on renal replacement therapy with hemodialysis.
- b) **Catheter affiliation variables** - design (twin or single), material (carbonate or polyurethane), date of insertion, date of removal, vein of insertion, previous catheter-related infections (bacteremia, tunnelitis, exit site infection).

c) **Catheter-related infections** during the follow-up period- will be defined as:

- *Bacteremia*- presence of fever (body temperature  $\geq 38^{\circ}\text{C}$ ) along with a positive blood culture, with no other focus of infection.
- *Exit site infection*- positive culture of pericatheter smear together with presence of inflammatory signs limited to 2 cm around the cutaneous exit site, with no upper extension to the catheter cuff if tunneled.
- *Tunnelitis*- appearance of inflammatory signs extending beyond 2 cm from the cutaneous exit site and in the subcutaneous tract of the catheter (tunnelitis). It may or may not be associated with fever and bacteremia, and may be accompanied by purulent exudate through the cutaneous exit site.

In case of clinical suspicion of bateremia due to fever (body temperature  $\geq 38^{\circ}\text{C}$ ), 2 blood cultures will be taken 30 minutes apart, from aerobic and anaerobic germs, directly from the arterial branch of the catheter.

The exit orifice will be inspected at each dressing, and the nurse in charge will take a photograph of it before performing the dressing, to check for the presence of signs of infection by the investigating team. In the presence of signs of infection, a culture of the pericatheter smear will be taken before the exit site is cured.

d) **Patient satisfaction** with the treatment regimen. - Patients will be surveyed after the follow-up period of the study about discomfort related to the type of treatment: pain on withdrawal, presence of pruritus, loss of adherence, alteration of body image, degree of comfort. To assess these aspects, SCALE 18 Degree of perception of positive expectations, of the NOC taxonomy (5-point Likert-type scale where 1- Not at all satisfied, 2- Somewhat satisfied, 3- Moderately satisfied, 4- Very satisfied, 5- Completely satisfied) will be used.

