e) Incidence of dressing-related skin alterations. - will be assessed at each hemodialysis session, using the following NOCs:

- [110115] Skin lesions
- [110121] Erythema

SCALE 14 Degree of a negative or adverse condition or response (Severe - Substantial - Moderate - Mild - None)

**Data collection and analysis:** An Excel-type data collection sheet will be created with the variables to be studied. The variables will be introduced by a member of the research team and will be extracted from the patients' clinical records (clinical reports, dialysis evolution sheets, catheter evolution sheets and analytical results). The survey of satisfaction with the treatment will be carried out by a member of the research team at the end of the follow-up period.

A descriptive analysis of the variables under study will be performed: in the case of quantitative variables, measures of central tendency and dispersion appropriate to the distribution and their 95% confidence intervals will be calculated; in the case of categorical variables, the frequency and percentage will be calculated. The catheter-related infection rate (bacteremia, exit site infection and tunnelitis) will be calculated using the following formula: number of catheter-related infections/ days of follow-up  $\times 1000$ ; both for the total number and by intervention group and type of catheter. In the case of comparisons between categorical variables, the chi-square test or Fisher's exact test will be used when necessary. Continuous variables will be compared using Student's t-test or Mann Whitney U-test, depending on their distribution. For the study of variables associated with the presence of catheter-related infections, a multiple logistic regression analysis will be performed including as independent variables age, sex, etiology of renal disease, degree of comorbidity, time on renal replacement therapy with hemodialysis,

type and model of catheter, duration of the catheter, location, and presence of previous catheter-related infections. The results will be considered significant if the critical level observed is less than 5% ( $p<0.05$ ). Statistical analysis will be performed with the PSPP statistical package.

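### The one multiple logistic model has 9 or 10 listed predictors for about 7 expected infected patients, so its odds ratios will be unstable or not estimable

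*Combined protocol and SAP*

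**What the plan says.** The secondary hypothesis names four factors expected to go with more infections: comorbidity, previous infections, time on renal replacement therapy and catheter duration. A secondary objective is to study such factors. Data collection and analysis assigns the question to one model: "a multiple logistic regression analysis will be performed including as independent variables age, sex, etiology of renal disease, degree of comorbidity", then time on dialysis, then "type and model of catheter, duration of the catheter, location, and presence of previous catheter-related infections". The same sentence gives the model's purpose: "For the study of variables associated with the presence of catheter-related infections". The plan mentions no variable selection, merging of categories or penalised estimation.

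Two predictors are loosely defined. Type and model of catheter can be one item or two; the catheter variables recorded are "design (twin or single), material (carbonate or polyurethane), date of insertion, date of removal, vein of insertion, previous catheter-related infections". Duration of the catheter has no stated end date. Etiology is recorded by ERA/EDTA code and so has several categories.

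The Population paragraph plans 25 patients per arm for a proportion "which for the control group is expected to be 25% and the experimental group 5" per cent, and adds: "A loss-to-follow-up rate of 10% has been estimated". It does not name the event to which the two proportions refer.

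**The concern.** A logistic model draws its information mainly from the rarer outcome, here the infected patients. If there are fewer of them than coefficients, maximum likelihood often has no finite solution, because some combination of predictors separates infected from uninfected patients perfectly. When a solution exists, odds ratios tend to be exaggerated and their intervals very wide.

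This is the only multivariable analysis planned for the secondary objective and the four-factor hypothesis. A non-significant result could be read as absence of association, and a significant one would probably be too large. The limitations section gives only the short follow-up as the main limitation and does not mention the small number of events.

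**Working it through.** **Inputs.** 25 + 25 patients, 25% and 5%, 10% loss (Population); 9 or 10 predictors (Data collection and analysis). The plan gives no expected number of events, so it has no figure to reproduce on this point. The two proportions are read as patients with at least one infection.

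**Expected events**
- No loss: 25 × 0.25 + 25 × 0.05 = 7.5. After 10% loss: 7.5 × 0.9 = 6.75.
- Per listed predictor: 6.75/10 = 0.68 to 7.5/9 = 0.83.
- With 25% in both arms: 50 × 0.25 = 12.5 events, or 1.25 to 1.39 per predictor. The conclusion does not depend on the treatment effect.

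**Distribution of events** (exact sum of two binomials)
- 25 + 25: P(fewer than 9) = 0.672; P(fewer than 10) = 0.799; 95% range 3 to 12.
- 22 control + 23 experimental (mean 22 × 0.25 + 23 × 0.05 = 6.65): 0.796 and 0.891; range 3 to 11.

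**Trials with no finite estimates** (simulated, no true covariate effects, independent covariates). The documents give no covariate distributions, so all are assumed.

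| Assumed predictors | 25 + 25 | 22 + 23 |
|---|---|---|
| 9 normal | 6.7% | 14.0% |
| 10 normal | 11.5% | 18.8% |
| 4 normal, 5 binary at 50% | 14.9% | 23.3% |
| 4 normal, 6 binary at 50% | 19.0% | 27.0% |
| 4 normal, 6 binary at 30–50% | 31% | 38% |
| Etiology 5 levels, location 3 levels | 76–90% | 85–93% |

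The last row gives ranges because several sets of category frequencies were tried. With six binary factors at 20% prevalence, failure was 70–80%. A hand check agrees: with 7 infected patients, the chance that none has a given 20% factor is 0.8^7 = 0.21, and for at least one of six such factors it is 1 − 0.79^6 = 0.76.

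**Planned model when one factor has a true odds ratio of 2 per SD** (maximum likelihood, Wald test, failed fits counted as not significant; in the order 9 normal / 10 normal / 4 normal with 6 binary at 50%)
- 25 + 25: failed 10.5 / 15.7 / 21.2%; median OR 2.44 / 2.51 / 2.44; upper quartile 4.27 / 4.61 / 4.89; power 19.3 / 15.6 / 15.5%.
- 22 + 23: failed 18.3 / 25.6 / 32.3%; median OR 2.52 / 2.59 / 2.56; upper quartile 5.14 / 5.72 / 5.67; power 12.4 / 9.7 / 10.6%.
- With no effect, Wald tests rejected in 2% to 4% of trials, so false positives are not inflated.

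**Alternative: Firth model with dressing group and one normal factor** (2,000 trials per setting, profile penalised likelihood)
- 25 + 25: median OR 1.96 (IQR 1.47–2.67), power 34.1%, null rejection 4.6%, coverage 95.5–95.7%.
- 22 + 23: median OR 1.91 (IQR 1.42–2.74), power 29.1%, null rejection 4.4%, coverage 95.0–95.6%.
- Penalisation is needed even here. The chance of no infection in the experimental arm is 0.95^25 = 27.7% (0.95^23 = 30.7%), and the ordinary estimate for dressing group is then infinite.

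**The case against.** The strongest reply is that the shortage of events, not the model, is the main reason a real factor would be missed. This is largely true: the Firth models still miss an odds ratio of 2 per SD in 66% to 71% of trials. What the planned model adds is failed fits, exaggerated estimates and a further loss of about half the power.

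Second, the plan already contains simpler tests: "In the case of comparisons between categorical variables, the chi-square test or Fisher's exact test will be used when necessary", with t or Mann-Whitney tests for continuous variables, and nothing limits these to comparisons between arms. For a continuous factor, Mann-Whitney has 31.3% power (28.3% at 22 + 23), close to Firth. This partly mitigates the problem. However, the plan names the multiple model for this question, and the tests give neither an odds ratio with an interval nor adjustment for dressing group.

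Third, one-factor models lose mutual adjustment. A factor with no effect of its own, correlated 0.3, 0.5 or 0.7 with a factor of odds ratio 2, shows a large-sample odds ratio of about 1.21, 1.39 or 1.60 and is significant in 6%, 11% or 19% of 25 + 25 trials. This cost is real.

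Fourth, the failure rates rest on assumed covariates. This stands for the exact percentages, but the simplest settings favour the plan. The 6.75 and 22 + 23 cases are also lower-end, since patients lost later may already have had an infection that counts.

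**Conclusion.** The concern holds. On the plan's own figures, 9 or 10 predictors face 7.5 infected patients (6.75 after loss), and more likely than not there will be fewer infected patients than predictors (67% to 89%). Fitted as written by ordinary maximum likelihood, the model will often fail, and otherwise give inflated, imprecise odds ratios. The event counts rest only on reading 25% and 5% as proportions of patients infected. The failure rates, odds ratios and power also depend on the assumed covariates. The damage is confined to the secondary objective on risk factors; the between-arm comparison is untouched. The plan should be changed here, but the trial's main result does not depend on it.

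**What to change.** Replace the model with four exploratory Firth-penalised logistic models, each with dressing group plus one factor from the secondary hypothesis: comorbidity, previous infections, time on renal replacement therapy, catheter duration. Report odds ratios with 95% confidence intervals, label them exploratory, and describe the other variables by infection status only.

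Define catheter duration as randomisation date minus insertion date. Counted to removal, it could be altered by the infection it is meant to predict. Also state whether "inserted 1 month prior to inclusion in the study" means at least one month. Read literally, catheter age would hardly vary and its model would tell nothing.

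If mutual adjustment matters more, one Firth model with dressing group and all four factors is the alternative. Null rejection is 4% to 5% and coverage about 96%, but power falls to 16% to 27%.

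The cost is analysis wording and possibly a routine outside PSPP, the only package named; no new data are needed. Three limits remain: the one-factor models are not mutually adjusted; power is low (29% to 34% for an odds ratio of 2 per SD, 10% to 13% for a yes/no factor with odds ratio 2); and a Firth estimate can rarely be extreme (1 of 6,000 simulated trials had a coefficient above 10 in size).

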### **Secondary:**

- To evaluate factors related to the incidence of hemodialysis catheter-related infections.
- To evaluate the incidence of dressing-related skin alterations.
- To assess patient satisfaction with regard to the type of hemodialysis catheter exit site dressing.

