#### **Causes of patient loss:**

- Exitus.
- Renal transplantation
- Use of arteriovenous fistula as vascular access.
- Transfer to peritoneal dialysis program.
- Hypersensitivity reaction to chlorhexidine gluconate.
- Exit from hemodialysis program due to other clinical situations.

**Follow-up period:** Patients carrying an indwelling catheter: 3 months.

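### The only multivariable model of infection omits the randomised dressing, the one factor with a stated effect size; the harm is modest, but the term belongs in a small penalised model

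*Combined protocol and SAP*

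**What the plan says.** Under Objectives, the first secondary objective is "To evaluate factors related to the incidence of hemodialysis catheter-related infections". The first secondary hypothesis names four such factors: comorbidity, previous infections, time on renal replacement therapy and catheter duration. No effect sizes are given for them.

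The Data collection and analysis paragraph answers this with one model: "a multiple logistic regression analysis will be performed including as independent variables age, sex, etiology of renal disease, degree of comorbidity". The list continues with time on hemodialysis and ends with "type and model of catheter, duration of the catheter, location, and presence of previous catheter-related infections". Treatment group does not appear, and no other adjusted analysis is described. The arms are compared through infection rates per 1000 days by group and through unadjusted tests.

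The Population paragraph gives the design figures. On size: "Fifty patients will be included (25 patients in the control group", with 25 in the experimental group. On infection proportions: "which for the control group is expected to be 25% and the experimental group 5"%. On attrition: "A loss-to-follow-up rate of 10% has been estimated". Follow-up is three months.

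**The concern.** The model's declared purpose is to find variables associated with infection, and the primary hypothesis is that the dressing is one of them. Pooling both arms while ignoring a factor planned at 25% against 5% has two consequences:

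- **Attenuation.** Odds ratios are non-collapsible. Leaving out a strong predictor pulls the odds ratios of other factors towards 1, even when those factors are perfectly balanced between arms.
- **Chance confounding.** A factor that happens to be commoner among controls picks up part of the dressing effect; one commoner in the experimental arm loses part of its own. The Design paragraph describes no stratification, so nothing prevents such splits in arms of 25.

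At stake is the answer to the first secondary hypothesis. The plan also yields no estimate of the dressing effect adjusted for, say, previous infection.

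**Working it through.** **Inputs from the plan.** 25 patients per arm; infection 25% and 5%; loss 10%; the listed covariates. The plan gives no covariate effect sizes or prevalences, so those below are assumptions. I take 25 per arm as given. From the plan's own inputs ("accepting an alpha risk of 0.05 and a beta risk of 0.2 in a bilateral contrast"), the usual pooled formula gives 49 per arm before loss, so the stated total is not reproduced; that is a separate matter.

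**1. Planned dressing effect.** (0.25/0.75) / (0.05/0.95) = 6.33.

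**2. Attenuation of a balanced factor.** Assume a binary factor with 50% prevalence in each arm and a true within-arm odds ratio of 3. Solving for the within-arm risks that average to 25% and 5%:

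| Arm | Factor absent | Factor present |
|---|---|---|
| Control | 15.1% | 34.9% |
| Experimental | 2.6% | 7.4% |
| Pooled | 8.9% | 21.1% |

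Pooled odds ratio: (0.2113/0.7887) / (0.0887/0.9113) = 2.75. By the same method 2 becomes 1.89 and 5 becomes 4.42, a shrinkage of about 8% on the log scale. For a normally distributed covariate with an odds ratio of 1.5 to 5 per SD, the shrinkage is 9 to 15%.

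*Against sampling error.* The bias is ln 3 − ln 2.75 = 0.09. Expected cell counts with 25 exposed and 25 unexposed are 5.28, 19.72, 2.22 and 22.78, so SE(log OR) = √(1/5.28 + 1/19.72 + 1/2.22 + 1/22.78) = 0.86. The bias is about a tenth of that.

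**3. Chance imbalance of a null factor.** Assume 25 of the 50 patients carry the factor, 15 in control and 10 in experimental.

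- Risk with the factor: (15 × 0.25 + 10 × 0.05)/25 = 0.170.
- Risk without it: (10 × 0.25 + 15 × 0.05)/25 = 0.130.
- Odds ratio: (0.170/0.830)/(0.130/0.870) = 1.37. A 16/9 split gives 1.56 and 17/8 gives 1.78.
- Hypergeometric probability of 15 or more in control: 0.129. The mirror-image split has the same probability, so 0.258 in either direction.

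*Against sampling error.* ln 1.37 = 0.32. With expected cells 4.25, 20.75, 3.25 and 21.75, SE = 0.80.

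*False positives.* Simulating a null factor in 25 of 50 patients, a univariable chi-square test that ignores arm rejects in between 5 and 6% of trials at the nominal 5%. Stratifying by arm gives 4.9%. Among trials with 15 or more exposed patients in control, the test ignoring arm rejects in about 7%.

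**4. Room in the model.** Expected infected patients: 25 × 0.25 + 25 × 0.05 = 7.5, or 6.75 after 10% loss. The list needs at least 9 to 10 parameters, so 0.75 to 0.83 events per parameter. Adding dressing on top gives 10 to 11 parameters and 0.68 to 0.75. Dressing plus only the four hypothesised factors, one term each, gives 7.5/5 = 1.5.

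**5. Separation.** P(no infected patient in the experimental arm) = 0.95^25 = 0.28; with 22 patients followed, 0.95^22 = 0.32. In that event the maximum-likelihood odds ratio for dressing is infinite.

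**The case against.** The strongest reply is that this matters little. Randomisation makes dressing independent of baseline factors on average, and both effects are small beside the standard errors. An odds ratio averaged over arms is also a different estimand rather than simply a wrong one. The model serves an exploratory objective and already has fewer than one expected event per parameter, so adding a term could make it worse. Most of this stands. It limits the size of the point and changes the remedy, but it does not make the omission a good choice: the variable is already held, and any sensible reduction of the model would still put the design factor in first.

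Three stronger readings are tempting and not supported:

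- *That the trial expects dressing to be the strongest predictor.* The plan never ranks it against the four hypothesised factors. It is only the one factor with a stated effect size.
- *That the risk-factor odds ratios are seriously distorted.* The figures show modest attenuation and a small excess of false positives.
- *That lacking an adjusted dressing effect undermines the primary result.* An unadjusted randomised comparison is valid, and the plan never promises an adjusted one.

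**Conclusion.** The point holds in limited form. The sole multivariable model leaves out a factor that the plan itself sets at an odds ratio of 6.33. The expected cost is roughly 8 to 15% shrinkage of log odds ratios, plus some exposure to chance imbalance, both below the sampling error of a 50-patient trial. The primary comparison is untouched. The sizes rest on the planned 25% and 5% being realised and on assumed covariate effects (odds ratios 1.5 to 5) and, for binary factors, 50% prevalence. It is worth correcting because a better specification is available from data already collected, and settling it now avoids a decision about adjusting for arm after the results are seen. It is a secondary-analysis improvement, not a threat to the trial's main conclusion.

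**What to change.** In the Data collection and analysis paragraph:

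1. Name randomised group, as assigned, as a forced term in the logistic model.
2. Let it take the place of predictors outside the first secondary hypothesis, so that the model holds dressing plus at most the four hypothesised factors. Do not add it to the full list.
3. Fit by Firth penalised likelihood, so that estimates stay finite if the experimental arm has no infected patient.
4. Report the adjusted dressing odds ratio with its 95% confidence interval, labelled as supportive of the unadjusted comparison.

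The cost is one degree of freedom, fewer exploratory predictors, and possibly software other than PSPP for the penalised fit. No new data or patients are needed. Even the five-term model has only about 1.5 expected events per parameter, so its results should still be described as exploratory.

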### **Secondary:**

- The degree of comorbidity, previous infections, time on renal replacement therapy, and catheter duration will correlate with a higher rate of catheter-related infections.
- Hemodialysis catheter exit site dressing with AGC dressings will correlate with higher patient satisfaction than dressing with 2% chlorhexidine solution and covered with a self-adhesive semi-permeable polyurethane dressing.

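### Catheter duration is a predictor of infection but is not fixed at baseline; if it is counted to removal, infection can shorten it and bias the association against the hypothesis

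*Combined protocol and SAP*

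**What the plan says.** All references are to the combined protocol and SAP.

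- **Hypothesis, Secondary:** "The degree of comorbidity, previous infections, time on renal replacement therapy, and catheter duration will correlate with a higher rate of catheter-related infections".
- **Variables, item b (catheter variables):** the catheter dates to be recorded are covered by "date of insertion, date of removal, vein of insertion". No duration variable is listed or defined.
- **Variables, item c:** infections are those occurring "during the follow-up period- will be defined as" the three listed types.
- **Data collection and analysis:** "For the study of variables associated with the presence of catheter-related infections, a multiple logistic regression analysis will be performed". Its predictors include "type and model of catheter, duration of the catheter, location, and presence of previous catheter-related infections". No start point, end point or unit is given for duration, and no value is given for a catheter still in place when follow-up ends.
- **Follow-up period:** "Patients carrying an indwelling catheter: 3 months".
- **Inclusion criteria:** "Be a carrier of a catheter as vascular access, inserted 1 month prior to inclusion in the study".

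Nothing in the plan says that infected catheters are removed, or how often. The list of causes of patient loss does not mention catheter removal.

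**The concern.** A predictor in a model for later infection should be known before the infection occurs. Catheter age at entry meets that condition. Time from insertion to removal, or to end of follow-up if the catheter stays in, does not, because part of it accrues after entry and can be cut short by the outcome. A catheter removed because of infection stops accruing time, while an uninfected one gains the full three months.

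The resulting bias has a known direction: infected patients appear to have shorter durations. That opposes the hypothesis. Duration is one of four factors the plan names, so the objective on factors related to infection could report a null or reversed association for it even if older catheters do carry more risk. The plan neither fixes duration at baseline nor makes it time-dependent. Because the removal date is listed beside the insertion date, the biased calculation is an easy one for an analyst to adopt.

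**Working it through.** The plan gives no figure for catheter duration, so there is none to reproduce. The check asks how far the association moves if duration is counted to removal.

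**Inputs from the plan**
- Expected infection 25% (control) and 5% (experimental), 25 patients each: overall (25% + 5%)/2 = 15%.
- Follow-up 3 months, taken as 91 days.
- Expected infected patients: 25 × 0.25 + 25 × 0.05 = 7.5, or 7.5 × 0.9 = 6.75 after the stated 10% loss.

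**Assumptions not in the plan**
- Proportion q of infected catheters removed at infection: 0, 25%, 50%, 100%.
- Catheter age at entry: uniform over 1–6, 1–12, 1–24 or 1–36 months.
- Constant infection hazard, unrelated to catheter age (no true effect).

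**Step 1: the shortening.** The hazard is λ = −ln(0.85)/91 = 0.001786 per day. Among infected patients the mean time to infection is 1/λ − 91 × 0.85/0.15 = 559.9 − 515.7 ≈ 44 days. A catheter removed at infection therefore loses on average 91 − 44 ≈ 47 days. The mean difference in duration, infected minus uninfected, is about −47q days.

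**Step 2: approximate odds ratio.** For a mean difference Δ and variance V, log OR per unit ≈ Δ/V. In 30-day months, Δ ≈ −1.56q. For ages uniform over 1–12 months, V = 11²/12 = 10.1. With q = 100%, log OR ≈ −1.56/10.1 = −0.154, so OR ≈ 0.86. For 1–24 months, V = 23²/12 = 44.1, log OR ≈ −0.035 and OR ≈ 0.97.

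**Step 3: simulation.** Logistic regression of infection on duration counted to removal or day 91, odds ratio per 30 days:

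| Age at entry | 0% removed | 25% | 50% | 100% |
|---|---|---|---|---|
| 1–6 months | 1.00 | 0.84 | 0.71 | 0.50 |
| 1–12 months | 1.00 | 0.96 | 0.93 | 0.86 |
| 1–24 months | 1.00 | 0.99 | 0.98 | 0.97 |
| 1–36 months | 1.00 | 1.00 | 0.99 | 0.985 |

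With age at entry as the predictor, the odds ratio is about 1.00 in every cell.

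**Step 4: other age distributions.** With log-normal ages and 90 days of follow-up, the odds ratio at 50% and 100% removed is 0.55 and 0.25 for a median age of about 90 days, 0.986 and 0.967 for about 210 days, and 0.997 and 0.994 for about 395 days. At a median of about 90 days, a true odds ratio of about 1.33 is estimated as 1.07, 0.80 and 0.42 with 25%, 50% and 100% removed.

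**Step 5: at the trial's size.** With 45 patients and no true effect, a Mann-Whitney comparison of duration counted to removal (a test the plan names for continuous variables) is significant at 5% in 28% and 74% of trials with 50% and 100% removed, at a median age of about 90 days. At about 210 days the figures are 8% and 15%; at about 395 days, 6% and 8%.

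**The case against.** The strongest reply is that the plan does not say what the concern needs it to say. Duration might mean insertion to inclusion, which carries none of this bias, and the removal date may be recorded for another purpose, such as counting follow-up days for the infection rate. Nothing states that infection leads to removal; the plan prescribes cultures on suspicion and is silent on what follows. At 0% removal there is no differential shortening. Shortening cannot exceed about three months, so for catheters in place for a year or more it is negligible. The analysis is also a secondary, observational one.

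Most of this stands, and it limits the point. A reader might infer that infection does shorten the tested variable in this trial. The documents do not support that, because they neither define duration as insertion to removal nor report any removal for infection.

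A reader might also take the entry criterion to mean exactly one month. All catheters would then start at the same age, and nearly all variation in duration would arise after entry. That reading is strained. It would limit a unit's existing catheter patients to catheters of one age and leave the duration hypothesis little to test, while the plan also records previous catheter-related infections. The wording needs clarifying, but it does not establish a worst case.

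What the reply does not remove is that a named predictor is not tied to a time before the outcome, and that one available calculation from the listed dates is biased. The plan gives no catheter ages or removal rate that would rule out the serious case.

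**Conclusion.** The point holds conditionally. Catheter duration is not fixed at baseline. If it is counted to removal or end of follow-up, and some infected catheters are removed, the association is biased against the hypothesis. With no true effect, the odds ratio per 30 days falls to between 0.84 and 0.50 for catheters aged 1–6 months at entry, but only to between 0.99 and 0.97 for 1–24 months, across removal of 25% to 100%. The size rests on an assumed removal proportion and assumed catheter ages, neither of which is in the plan.

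The randomised comparison is untouched. Even with duration well defined, about 7 infected patients against nine listed predictors (age, sex, etiology, comorbidity, time on therapy, catheter type and model, duration, location, previous infections) leaves every coefficient imprecise. The correction removes an avoidable bias; it does not make that model reliable.

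**What to change.** - **Secondary hypothesis, and Data collection and analysis:** replace catheter duration with catheter age at randomisation, defined as randomisation date minus insertion date, with the unit stated.
- **Data collection and analysis:** state that the removal date is not used to build any predictor.
- **Inclusion criteria:** state whether the one-month condition means at least one month.

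This makes the question whether older catheters at entry have more infections over the next three months. If the investigators mean time accrued during follow-up, a time-dependent analysis would be the alternative and should be specified as such.

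The cost is wording in three places. The insertion date is already collected and the randomisation date arises from trial conduct, so no further clinical data are needed.
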